### PASS Information

Title	Retrospective Drug Utilisation Study to investigate the routine use of Hydroxyethyl Starch (HES)-containing Infusion Solutions in Hospitals
Protocol Version Identifier	HES DUS Protocol_Version 1.4_07 May 2015
Date of Last Version of Protocol	07 May 2015
EU PAS Register Number	Will be submitted after finalisation of protocol and approval by the PRAC
Active Substances	Fresenius Kabi Deutschland GmbH:  Poly(O-2-hydroxyethyl)starch  Sodium chloride Sodium acetate trihydrate (for Volulyte) Potassium chloride (for Volulyte) Magnesium chloride hexahydrate (for Volulyte)  ATC code:  Blood substitutes and plasma protein fractions B05AA07 hydroxyethylstarch

Medicinal Products	Fresenius Kabi Deutschland GmbH: The registered product name for the individual products concerned in the European countries in which the DUS will be conducted is provided in Annex 1a.
Product Reference	Not applicable
Procedure Numbers	Fresenius Kabi Deutschland GmbH: DE/H/223/01; DE/H/1568/001/DC; DE/H/0619/01/DC; DE/H/295/01
Marketing Authorisation Holder(s)	Fresenius Kabi Deutschland GmbH [name] Germany  Note: The registered marketing authorisation holder for the individual products in the European countries in which the DUS will be conducted is provided in Annex 1a.

Joint PASS	No
Research Question and Objectives	The objective of the Drug Utilisation Study (DUS) is to assess the adherence of hospital physicians to the revised European Product Information (PI) [Summary of Product Characteristics (SmPC); Package Leaflet] for Hydroxyethyl Starch (HES) - containing medicinal products concerning indication, posology (dosage) and contraindications (as listed in Annex III of the EC decision).
Country(-ies) of Study	Intended countries for conduct of DUS: Belgium, Czech Republic, France, Germany, Netherlands, Poland, Spain, Sweden, United Kingdom
Author	Fresenius Kabi  Main author: 

## 2. List of Abbreviations

AHRQ	Agency for Healthcare Research and Quality
ATC	Anatomic Therapeutic Chemical classification
CMDh	Coordination Group for Mutual Recognition and Decentralised Procedures human
CRF	Case Report Form
CRO	Contract Research Organisation
DUS	Drug Utilisation Study
eCRF	Electronic Case Report Form
EC	European Commission
e.g.	Example given
EMA	European Medicines Agency
ENCePP	European Network of Centers for Pharmacoepidemiology and Pharmacovigilance
EU	European Union
EU PAS Register	EU electronic register of post-authorisation studies
EU-QPPV	European Union - Qualified Person Responsible For Pharmacovigilance
GVP	Good Pharmacovigilance Practice
GPP	Good Pharmacoepidemiology Practice
HES	Hydroxyethyl Starch
ICD-10	International Classification of Disease, tenth revision
i.e.	Id est, that is
IEC	Independent Ethics Committee
ICU	Intensive Care Unit
ISPE	International Society of Pharmaceutical Engineering
MAH	Marketing Authorisation Holder
MedDRA	Medical Dictionary for Regulatory Activities
NCA	National Competent Authorities
NYHA	New York Heart Association
PASS	Post-authorisation safety study
PRAC	Pharmacovigilance Risk Assessment Committee
PDMS	Patient Data Management System
PI	Product Information
PICU	Paediatric Intensive Care Unit
PRAC	Pharmacovigilance Risk Assessment Committee
SmPC	Summary of Product Characteristics
SAP	Statistical Analysis Plan

### 3. Responsible Parties

This Drug Utilisation Study (DUS) will be conducted by Fresenius Kabi Deutschland GmbH, [name] (Germany), as concerned marketing authorisation holder (MAH).

Contact persons for Fresenius Kabi Deutschland GmbH:

- [REDACTED]

For this DUS, HES products of Fresenius Kabi, registered in those countries in which the DUS is performed, will be included. Fresenius Kabi as responsible MAH will monitor the progress of the DUS and receive status reports from the CRO concerning the number of documented patients. Due to the non-interventional and the retrospective design of the DUS, Fresenius Kabi will not have any influence on the treatment of the patients.

A **Contract Research Organisation (CRO)** will provide all logistical and regulatory support for the study, observe data quality, host the database and analyse the data and write the final study report. Further details about the respective task allocation between the Fresenius Kabi and the CRO are defined in a task allocation list which is part of the contract with the CRO.

CRO contact details:

[REDACTED]

A **principal investigator** for each site will be assigned before the first patient will be documented in the DUS in the respective country. If required by local law, a **coordinating investigator** in participating countries will be additionally assigned. Contact details and a list of all investigators and participating sites will be kept in a stand-alone document (see Annex 1b).

#### **4. Abstract**

##### **Title**

Retrospective Drug Utilisation Study to investigate the routine use of Hydroxyethyl Starch (HES)-containing Infusion Solutions in Hospitals

##### **Protocol Version**

Version 1.4, 07 May 2015

##### **Date of the Protocol**

07 May 2015

##### **Rationale and Background**

The European Medicines Agency (EMA) Pharmacovigilance Risk Assessment Committee (PRAC) recommended in the Article 107i procedure according to Directive 2001/83/EC for HES-containing medicinal products (EMA/H/A-107i/1376) in October 2013 that HES solutions must no longer be used to treat patients with sepsis or burn injuries or critically ill patients because of an increased risk of kidney injury and mortality while the benefit-risk ratio for HES-containing medicinal products remains favourable in the treatment of hypovolaemia due to acute blood loss when crystalloids alone are not considered sufficient.

The final implementing decision, issued by the European Commission (EC) on December 19, 2013, implicates new contraindications, new special warnings and precautions for use as well as other changes to the European Product Information (PI) [Summary of Product Characteristics (SmPCs); Package Leaflet] for risk minimisation measures (as requested in Annex III of this EC decision).

To “evaluate the effectiveness of the risk minimisation measures taken” (as requested in Annex IV of the EC decision), the concerned MAHs of HES products subject to the PRAC procedure were asked to conduct a Drug Utilisation Study (DUS) with HES-containing medicinal products in several European Union (EU) Member States.

##### **Research Question and Objectives**

The objective of the DUS is to assess the adherence of hospital physicians to the revised European PI for HES-containing medicinal products concerning indication, posology (dosage) and contraindications (as listed in Annex III of the EC decision).

### **Study Design**

Retrospective, non-interventional, multinational, multi-centre DUS

### **Population**

Patients treated with HES-containing infusion solutions in hospitals in the intended 9 European countries.

### **Variables**

The DUS will document patient data describing the medical status at initiation of treatment, posology (dosage) and contraindications of HES to identify deviations from the revised European PI (as listed in Annex III of the EC decision).

### **Data Sources**

Data will be collected retrospectively from patients previously treated with HES within a defined timeframe using patient charts. Primarily, study sites that are using an electronic Patient Data Management System (PDMS) for patient data documentation will be chosen. Data will be entered into secure online electronic case report forms (eCRFs) by investigators or delegated responsible persons based on patient charts. All data will be fully anonymised.

### **Study Size**

In order to achieve sufficient precision of country-specific estimates of non-compliance to the revised European PI at least 334 patients per country are required. For nine countries, at least 3000 HES treated patients in total will be documented in the study.

### **Data Analysis**

Descriptive analysis will be performed on data collected and will include absolute numbers and proportion of adherence to the revised European PI for the overall population and subgroups. 95 % confidence intervals on proportions of adherence will be provided.

### **Milestones**

Start of retrospective data collection, i.e. “Date from which the data extraction from patient charts starts” – about 3 to 4 months after protocol approval by the PRAC and notification to national competent authorities (NCA) and positive Independent Ethics Committees (IEC) opinion as required by national and local regulations and requirements.

End of retrospective data collection, i.e. “Date from which the analytical data set is completely available” – about 9 to 12 months after start of data collection.

Final report of study results – will be submitted within 24 months of the final protocol approval by the PRAC.

## 5. Amendments and Updates

None

Number	Date	Section of study protocol	Amendment or update	Reason

## 6. Milestones

Milestone	Planned date
Start of data collection a	About 3 to 4 months after protocol approval by the PRAC and notification to NCAs and positive IEC opinion as required by national and local regulations and requirements.
End of data collection b	About 9 to 12 months after start of data collection.
Registration in the EU PAS Register	The DUS will be registered in the EU electronic register of post-authorisation studies (EU PAS Register) after final protocol approval by the PRAC and before the start of data collection.
Final report of study results	Will be submitted within 24 months of the final protocol approval by the PRAC.

a Date from which the data extraction from patient charts starts

b Date from which the analytical data set is completely available

## 7. Rationale and Background

Following the publication of investigator initiated clinical trials such as 6S (Perner et al. 2012), CHEST (Myburgh et al. 2012) and VISEP (Brunkhorst et al. 2008), comparing HES-containing solutions with crystalloids in critically ill patients (e.g. septic patients), the EMA, initiated procedures to assess the benefits and risks of HES-containing solutions, especially in critically ill patients.

In the relevant European referral procedure according to Article 107i of Directive 2001/83/EC for HES-containing medicinal product (EMEA/H/A-107i/1376) the PRAC, recommended in October 2013 that HES-solutions must no longer be used to treat patients with sepsis or burn injuries or critically ill patients because of an increased risk of kidney injury and mortality in these patients but that the benefit-risk ratio for HES-containing

medicinal products remains favourable in the treatment of hypovolaemia due to acute blood loss when crystalloids alone are not considered sufficient.

This recommendation was adopted by majority vote by the Coordination Group for Mutual Recognition and Decentralised Procedures human (CMDh). The final implementing decision was issued by the EC on December 19, 2013 by which this referral procedure was positively concluded. This implicates new contraindications, special warnings and precautions for use as well as other changes to the European PI for risk minimisation measures (as requested in Annex III of the EC decision).

In addition, the concerned MAHs were requested to conduct a DUS with HES-containing medicinal products in several EU Member States to “evaluate the effectiveness of the risk minimisation measures taken” (as requested in Annex IV of the EC decision).

The DUS will be performed by the MAH Fresenius Kabi Deutschland GmbH and will include all available HES-containing medicinal products of this MAH in those European countries where the DUS will be performed. A detailed overview about the concerned medicinal products in the individual country is provided in Annex 1a.

In summary, the scope of this DUS is to investigate the adherence of hospital physicians to the revised European PI for HES-containing medicinal products during routine administration of HES-solutions in hospitals to evaluate the effectiveness of the risk minimisation measures taken.

## **8. Research Question and Objectives**

The objective of the DUS is to assess the adherence of hospital physicians to the revised European PI for HES-containing medicinal products concerning indication, posology (dosage), and contraindications (as listed in Annex III of the EC decision).

In general, due to its retrospective and non-interventional nature the DUS can only be used to generate hypotheses and not to test any a-priori specified hypothesis.

## **9. Research Methods**

### **9.1 Study Design**

The study is a retrospective, non-interventional, multinational, multi-centre European DUS of use of HES-containing medicinal products in hospitals. The DUS will follow national laws and regulations.

Outcome measure is the adherence to the concerned sections of the revised European PI for HES-containing medicinal products.

Usage of these medicinal products according to indications, posology (dosage), and contraindications as specified in the revised PI of the HES solutions will be assessed.

In the DUS, routine clinical use of HES-containing medicinal products of Fresenius Kabi will be documented by retrospective data collection from patient charts within a predefined timeframe. Retrospective data collection best reflects actual patterns of use and allows reducing bias as described in [Section 9.9](#) to a minimum. To ensure that there is a very high coverage of patients administered HES containing products, site selection will focus on sites using electronic PDMS. Patient charts will be thoroughly searched via free text, ICD-10 code (diagnosis), and ATC code (medication) to ensure identification of eligible patients as complete as possible.

Following the final approval of the submitted protocol by the PRAC, notification to NCAs and positive IEC opinion as required by national and local regulations and requirements, as well as the administrative processes such as site selection and contracting of sites will be initiated.

The retrospective data collection will comprise patient chart data of patients who have been treated between January 1st, 2015 and May 1st, 2015. Patient chart data will be collected going backwards in a predefined timeframe, e.g. of one week (depending on the results of the site feasibility), starting May 1st, 2015 (calendar week 18). All patients treated with HES-containing products of Fresenius Kabi during this week should be documented. In the event that the predefined number of patients per site is not achieved within e.g. this week, data collection can be extended e.g. week by week (again going backwards) until the number of predefined patients has been reached, but not beyond January 1st, 2015. All patients treated with HES-containing products of Fresenius Kabi within the predefined timeframe are documented in the DUS and followed-up until the start and end of HES therapy, even if the start or end of HES therapy are outside the predefined timeframe.

Data collection will include relevant demographic data, main diagnosis at hospital admission, indication for HES use, posology (dosage), and co-morbidities.

The parameters as listed in [Section 9.3](#) will be documented.

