### 9.2.1 Countries, Feasibility and Site Selection

The DUS is intended to be conducted in the following European Member States: Belgium, Czech Republic, France, Germany, Netherlands, Poland, Spain, Sweden, United Kingdom. In order to reduce potential bias from site specific clinical practice it is aimed that per country, at least 5 sites will be included expecting a minimum of about 67 eligible patients per site (depending on the outcome of the feasibility). The sites can only participate upon agreeing to the requested procedures in the participating sites as specified in [Section 9.8.1](#).

Prior to the start of the DUS, a feasibility check/survey will be performed by the CRO to evaluate e.g.

- whether the sites use HES-containing medicinal products from Fresenius Kabi,
- how frequently HES-containing medicinal products from Fresenius Kabi have been used,
- whether the sites use electronic PDMS,
- whether all wards or, if this is not the case, which wards in the hospitals use electronic PDMS,
- which wards have been supplied with HES from Fresenius Kabi within the sites,
- whether the sites collect general consent for using patients' data for research projects,
- whether the sites are willing to participate.

For the retrospective data collection in this DUS, sites using electronic PDMS will be preferred since PDMS allow the comprehensive review of all patient charts at the site regarding administration of HES products in the given retrospective data collection period. Thus, the selection process for sites using HES-containing medicinal products from Fresenius Kabi will be performed following a hierarchic stepwise process as described below:

- (1) HES use and full PDMS coverage within data collection period
- (2) HES use and PDMS use in all wards which have been identified in the survey to be supplied with HES within data collection period
- (3) HES use and PDMS use or paper documentation in all wards which have been identified in the survey to be supplied with HES within data collection period (applies to sites with partial PDMS coverage in HES using wards)
- (4) Sites or wards with HES use within data collection period but paper documentation only

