For sites not (completely) using PDMS, the sites' pharmacies will be contacted by the CRO, as part of the feasibility check/survey, to identify the wards which had been supplied with HES from Fresenius Kabi to ensure a high coverage of patients that had received HES. This procedure and the results will be thoroughly documented by the CRO.

After each selection step as described above, identified study sites will be randomly selected per country in case the selection process reveals more than the intended total number of sites.

---

If despite all above mentioned selection strategies the required number of about 334 patients per country cannot be documented within the predefined timeframe, the following measures will be taken in a further hierarchic stepwise manner:

- (A) Extension of timeframe for data collection until November 1st, 2015 (if retrospective nature of the DUS is still ascertained)
- (B) Initiation of new sites in the respective country where 334 patients have not been documented
- (C) Inclusion of additional European countries that have not yet participated and fulfilling the selection criteria (e.g. minimum of 5 centres and sufficient patients)

All new countries and all new sites will be selected according to the feasibility criteria as described above.

All available data, including those from an initially included country where the required patient and/or site number could not be finally achieved, will be analysed in a descriptive manner.

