### **9.2.3 Inclusion Criteria**

- Patients who were receiving any of the HES-containing medicinal products listed in Annex 1a within the predefined timeframe will be documented in the DUS.

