## 9.5 Study Size

For determining the number of patients that should be documented in this DUS it is aimed to achieve sufficient precision of estimates for the percentage of non-compliance to the PI. It is intended that all analyses will be performed for the overall population as well as for each country separately. Therefore, the chosen sample size needs to have sufficient precision also for the country-specific estimates.

For potential non-compliance rates in the interval of 1 % to 4 % the expected precision (95 % confidence intervals) for various sample sizes ranging from 100 to 3000 patients were calculated. The results are shown in Table 1.

Table 1: Expected 95 % confidence intervals for potential non-compliance rates in the intervals of 1 % to 4 % estimated in sample sizes of 100 to 3000 patients. Exact method (R function `binom.test{stats}`) used.

	Estimated rate 1 %	Estimated rate 2 %	Estimated rate 3 %	Estimated rate 4 %
N = 100	0.0 - 5.4 %	0.2 - 7.0 %	0.6 - 8.5 %	1.1 - 9.9 %
N = 334	0.2 - 2.6 %	0.8 - 4.3 %	1.4 - 5.4 %	2.1 - 6.6 %
N = 500	0.3 - 2.3 %	1.0 - 3.6 %	1.7 - 4.9 %	2.5 - 6.1 %
N = 1000	0.5 - 1.8 %	1.2 - 3.1 %	2.0 - 4.3 %	2.9 - 5.4 %
N = 1500	0.6 - 1.6 %	1.4 - 2.8 %	2.2 - 4.0 %	3.1 - 5.1 %
N = 2000	0.6 - 1.5 %	1.4 - 2.7 %	2.3 - 3.8 %	3.2 - 5.0 %
N = 2500	0.6 - 1.5 %	1.5 - 2.6 %	2.4 - 3.7 %	3.3 - 4.8 %
N = 3000	0.7 - 1.4 %	1.5 - 2.6 %	2.4 - 3.7 %	3.3 - 4.8 %

Considering the number of patients that is expected per country, it is intended to include at least 3000 patients in total (meaning 334 patients per country) in order to achieve sufficient precision of also country-specific estimates.

As an example, for an assumed non-compliance rate of 3 % and a sample size of 334 patients the expected 95 % confidence interval is 1.4 % to 5.4 %. For the intended sample size of overall 3000 patients the expected 95 % confidence interval is 2.4 % to 3.7 %.

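### Entry by overlap with a short, volume-dependent site window over-samples longer HES courses, so cumulative dose, and posology non-compliance if it rises with course length, may be overstated unequally across sites

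*Protocol*

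**What the plan says.** Section 9.2.3 has one inclusion criterion: "Patients who were receiving any of the HES-containing medicinal products listed in Annex 1a within the predefined timeframe". It asks that HES was received in the window, not that it was started there. Section 9.1 confirms this reading, because each included patient is traced to the beginning and end of therapy "even if the start or end of HES therapy are outside the predefined timeframe".

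The window is site-specific. Section 9.1 begins at 1 May 2015: "Patient chart data will be collected going backwards in a predefined timeframe, e.g. of one week". If the site's number is not met, "data collection can be extended e.g. week by week (again going backwards) until the number of predefined patients has been reached". The earliest date that this extension may reach is 1 January 2015. Section 9.2.1 sets the scale per site, "expecting a minimum of about 67 eligible patients per site", and adds a fallback for countries that fall short: "Extension of timeframe for data collection until November 1" (2015).

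The adherence domains in Sections 8 and 9.1 are indication, posology and contraindications. Section 9.7.1 adds cumulative and maximum daily dose, and plans results overall, by country and by site. Section 9.3.2 records relative day and clock time for the start and end of every bag. Admission and ward discharge are recorded as calendar weeks. Section 9.9 does not mention selection by course length.

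**The concern.** Entry by overlap is prevalent sampling. A patient treated for several days has more chances to fall in a given week than a patient treated once. The sample therefore describes patients on HES in the window, weighted towards long courses, and not HES courses as they are prescribed.

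This affects results the protocol names. A longer course adds cumulative dose and gives more days on which a daily limit could be exceeded, so the likely direction is upward. The strength depends on W, and W is set by site volume. Busy sites stop early and have the strongest over-sampling. Slow sites run towards 1 January and have almost none. Two sites with identical practice could report different dose profiles, and results are to be shown by site and country. Enrolling more patients does not remove this error.

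**Working it through.** **The plan's own figures.** Section 9.5 works with exact 95 % intervals: "For potential non-compliance rates in the interval of 1 % to 4" per cent. Clopper-Pearson limits with the count rounded to the nearest patient reproduce all 32 cells of Table 1. For 3 %, 10 of 334 gives 1.4 % to 5.4 %, and 90 of 3000 gives 2.4 % to 3.7 %. These serve as the yardstick below.

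**Inputs from the protocol.** The shortest window mentioned is W = 7 days, as an example. The longest before the fallback is 1 January to 1 May 2015, which is 121 days or about 17 weeks. At 67 patients per site, a one-week window needs about 67 HES patients a week, and the full window needs about 67/17 = 4 a week.

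**Assumed input.** D is the number of days from first to last infusion. The protocol gives no distribution, so a range is shown.

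**Inclusion weight.** With starts spread evenly over time, a D-day course overlaps a W-day window for W + D - 1 possible start days. Relative to a one-day course the weight is (W + D - 1)/W:

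| D (days) | W = 7 | W = 14 | W = 28 | W = 121 |
|---|---|---|---|---|
| 2 | 1.14 | 1.07 | 1.04 | 1.01 |
| 3 | 1.29 | 1.14 | 1.07 | 1.02 |
| 5 | 1.57 | 1.29 | 1.14 | 1.03 |
| 7 | 1.86 | 1.43 | 1.21 | 1.05 |

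**Effect on cumulative dose (assumed mix).** Suppose 5 % of courses last 5 days, the rest 1 day, with equal volume per day. At W = 7 the sampled share of 5-day courses is 0.05 × 11/(0.05 × 11 + 0.95 × 7) = 0.55/7.20 = 7.6 %. Mean treatment days, and so mean cumulative dose, rise from 0.95 × 1 + 0.05 × 5 = 1.20 to 0.924 × 1 + 0.076 × 5 = 1.31, about 9 %. At W = 121 the share is 6.25/121.2 = 5.2 % and the mean is 1.21.

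**Effect on non-compliance, extreme case.** Let every non-compliant course last D days and every other course 1 day, with true rate p = 3 %. The expected observed rate is p(W + D - 1)/[p(W + D - 1) + (1 - p)W].

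- W = 7, D = 2: 0.24/(0.24 + 6.79) = 3.4 %
- W = 7, D = 3: 0.27/(0.27 + 6.79) = 3.8 %
- W = 7, D = 5: 0.33/(0.33 + 6.79) = 4.6 %
- W = 7, D = 7: 0.39/(0.39 + 6.79) = 5.4 %
- W = 121, D = 2, 3, 5: 3.0 %, 3.0 %, 3.1 %

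A simulation at W = 7, D = 3 gave 3.9 % under overlap entry, 3.0 % when only starts inside the window counted, and 3.1 % under overlap entry with inverse weighting.

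**Effect on non-compliance, weaker dependence (assumed).** Let 5 % of courses last 5 days with 20 % non-compliance, and one-day courses have 2.1 %. The true rate is 0.05 × 0.20 + 0.95 × 0.021 = 3.0 %. At W = 7 the sample shows 0.076 × 0.20 + 0.924 × 0.021 = 3.5 %.

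**Against the yardstick.** If every site used one week, D = 3 in the extreme case (3.8 %) lies just above the N = 3000 upper limit of 3.7 %, and D = 2 (3.4 %) stays below it. At country level, N = 334, only about 7 days reaches the 5.4 % limit.

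**The case against.** The strongest reply is that overlap entry is deliberate. The protocol wants every patient treated in the window, and Section 9.7.1 estimates coverage from the average weekly HES amount. Entry by start drops carry-over patients who did use HES in that week. The study is also descriptive, with no formal site or country comparison, and a later SAP could add weighting. This stands in part. Completeness is a legitimate aim and the loss of carry-over patients is a real cost. But complete capture of a week's users does not give a representative picture of courses, which is what posology adherence is judged on, and the entry rule is fixed in the protocol.

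Four stronger readings are tempting and should not be drawn.

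- A reader might infer that the bias is irreparable because no calendar date of first HES is recorded. That is wrong. Per-bag times give D, and with the site's window this allows weighting. Restricting to patients admitted inside the window is a further partial route, at the cost of patients.
- A reader might infer that duration non-compliance is overstated. Duration is not a named outcome, and the text at hand shows no duration limit.
- A reader might take it as settled that busy sites stop after one week. One week is an example that depends on site feasibility, and many sites may need longer.
- A reader might extend the claim to the whole adherence outcome. Nothing in the protocol shows that indication or contraindication adherence varies with course length.

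Recording whole courses is sound, because it avoids truncating dose. The fault lies in the entry rule.

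**Conclusion.** The point holds in a conditional form. That longer courses are over-sampled, most where windows are shortest, follows directly from Sections 9.1 and 9.2.3. No section corrects or acknowledges it, and the one bias given a direction in Section 9.9 is underestimation of amounts. Inflation of cumulative dose follows as soon as some courses span several days. Inflation of posology non-compliance further requires non-compliance to rise with course length, which is plausible but not documented.

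The size rests on assumed course lengths and steady starts. It ranges from nearly nothing, if almost all courses last a day, to about 0.4 to 1.6 percentage points on a true 3 % at a one-week site, if all non-compliant courses last 2 to 5 days and all others one day. At a site using the full window it is 0.1 points or less over the same range. The case for changing the rule is that the repair is cheap and the distortion is uneven across reported units, not that a large bias has been shown.

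**What to change.** In Section 9.2.3, define entry (or at least the main posology analysis set) as patients whose first HES infusion of the course started within the site's window. Keep the Section 9.1 rule that each course is documented to its end. Add to the eCRF the calendar week of first HES infusion, or an in-window-start flag set at the site, because infusion days are relative. Record each site's final window.

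If overlap entry is kept for completeness, weight each patient by W/(W + D - 1) in the dose and posology analyses, using the per-bag times and the recorded window. In that case, list selection by course length in Section 9.9.

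The cost is one sentence and one or two fields. A few carry-over patients are lost per window and can be replaced through the planned backward extension. The coverage calculation in Section 9.7.1 must use the same entry definition in numerator and denominator.
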